5.2.3.4 Treatment for Cytokine Release Syndrome

Table 15 Cytokine Release Syndrome Treatment Guidelines

NCI CTCAE Grade	Treatment	Premedication at subsequent dosing
Grade 1 Mild reaction: Therapy interruption not indicated. Intervention not indicated.	Increase monitoring of vital signs and oxygen saturation, as medically indicated, until the subject is deemed medically stable in the opinion of the investigator	None
Grade 2 Therapy interruption indicated but responds promptly to symptomatic treatment (eg, NSAIDS, narcotics, IV fluids). Prophylactic medications indicated for ≤ 24 hours	Increase monitoring of vital signs and oxygen saturation, as medically indicated, until the subject is deemed medically stable in the opinion of the investigator Additional appropriate medical therapy may include, but is not limited to: IV fluids NSAIDS Acetaminophen Narcotics Oxygen Perform fever workup to exclude	Subject may be premedicated 1.5 hours (± 30 minutes) prior to MK-1454 administration with acetaminophen 500 to 1000 mg po (or equivalent dose of antipyretic)
0.1.0	infectious etiologies; treat neutropenia if present	E. G. La GDG II
Grade 3 Prolonged (eg, not rapidly responsive to symptomatic medication); recurrence of symptoms following initial improvement; hospitalization indicated for clinical sequelae (eg, renal impairment, pulmonary infiltrates)	Additional appropriate medical therapy may include, but is not limited to: IV fluids NSAIDS Acetaminophen Narcotics Oxygen Pressors Corticosteroids Anti-IL6 (eg tocilizumab) Empiric antibiotics	For Grade 3 CRS, discuss with Sponsor prior to restart of MK-1454 treatment. Upon approval by Sponsor, MK-1454 may be restarted at a reduced dose when AE resolves back to baseline or to Grade 1 (see Table 11). Subject may be premedicated 1.5 hours (± 30 minutes) prior to MK-1454 administration with acetaminophen 500 to 1000 mg po (or equivalent dose of
	Subjects with ≥ Grade 3 CRS need to be monitored very closely, likely in an intensive care setting	antipyretic)

Protocol/Amendment No.: 001-08

NCI CTCAE Grade	Treatment	Premedication at subsequent dosing
Grade 4	Additional appropriate medical	Permanently discontinue MK-
	therapy may include, but is not	1454 in subjects who develop
Life-threatening consequences;	limited to:	Grade 4 CRS
pressor or ventilatory support		
indicated	IV fluids	
	NSAIDS	
	Acetaminophen	
	Narcotics	
	Oxygen	
	Pressors	
	Corticosteroids	
	Anti-IL6 (eg tocilizumab)	
	Empiric antibiotics	
	1	
	Subjects with ≥ Grade 3 CRS need	
	to be monitored very closely, likely	
	in an intensive care setting	

Treatment by local surgery and/or radiation therapy of isolated or symptomatic progressing lesions in the setting of improving baseline disease may be permitted for palliative or potentially curative management following completion of Cycle 2. Subsequently, all interventions, including continuation of study drug, should be discussed with the Sponsor Medical Monitor or designee.

5.2.4 Intrasubject Dose Escalation

Intrasubject dose escalation will be allowed for subjects in Arm 1 (Parts A and B) monotherapy at the discretion of the investigator provided that the subject remains on study after receiving 3 cycles of treatment with MK-1454 monotherapy without a \geq Grade 2 drug-related toxicity, and provided that dose escalation has proceeded beyond the next dose level. The subject may undergo intrasubject dose escalation one time while enrolled in this treatment arm.

Subjects enrolled in the ATD phase of Arm 3 may undergo dose escalation one time after receiving 3 cycles of treatment without a \geq Grade 2 drug-related toxicity.

Intrasubject dose escalation is not permitted during the DLT evaluation period.

The subject may escalate to the highest dose level (and frequency for Arm 3) that has been cleared by DLT evaluation. This dose will be communicated to the site via written consent from the Sponsor and administered by IWRS. De-escalation from this dose will be based on occurrence of DLTs per dose escalation guidelines for either the ATD or the mTPI phase (see Section 5.2.1), as appropriate. Dose modification will be based on CTCAEs per Dose Modification Guidelines (see Section 5.2.3).

Protocol/Amendment No.: 001-08

5.2.5 Timing of Dose Administration

Each subject may undergo up to 35 cycles (approximately 2 years) of MK-1454 treatment in both the monotherapy arm (Arm 1) and the combination therapy arms (Arm 2 and Arm 3), as well as the Expansion Cohorts (Cohort A to C).

After C1D1, trial treatment may be administered up to 3 days before, or up to 3 days after the scheduled treatment day within each cycle. Dosing interruptions are permitted in the case of medical/surgical events or logistical reasons that are not related to study therapy (eg, elective surgery, unrelated medical events, patient vacation, and/or holidays). Subjects should be placed back on study therapy within 3 weeks of the scheduled interruption, unless otherwise discussed with the Sponsor Medical Monitor or designee. The reason for interruption should be documented in the subject's study record.

5.2.5.1 Timing of MK-1454 Dose Administration in Part I - Dose Escalation and Confirmation

MK-1454 will be administered on Day 1, Day 8, and Day 15 in each 21-day cycle for Cycles 1, 2, and 3 for Arms 1 and 2. Beginning with Cycle 4, MK-1454 will be administered on Day 1 of each 21-day cycle.

For Arm 3, MK-1454 will be administered IT to visceral lesions at escalating frequencies	es. Ir
the ATD phase, MK-1454 will be administered CCI	In the
mTPI phase, frequency of administration will begin with Escalation of frequency	/ may
proceed first to a CCI	on
Day 1 of Cycle 3 and beyond. Escalation of frequency may then proceed to	
After Cy	cle 3
frequency of visceral IT administration may be modified by the investigator based on cli	inica
assessment of the investigator and discussion with the Sponsor.	

In Arm 2 and Arm 3 of the trial, MK-1454 will be administered within 0.5 to 4 hours following completion of pembrolizumab infusion.

5.2.5.2 Timing of MK-1454 Dose Administration in Part II - Expansion Cohorts

In Cohorts A and B, MK-1454 IT will be administered on Day 1, Day 8, and Day 15 in each 21-day cycle for Cycles 1 and 2. Beginning with Cycle 3, MK-1454 will be administered on Day 1 of each 21-day cycle.

Cohort C will initiate MK-1454 visceral IT treatment at the dose and frequency established as the RP2D from Arm 3.

5.2.5.3 Timing of Pembrolizumab Administration

Pembrolizumab 200 mg will be administered as an IV infusion on Day 1 of each 21-day cycle, in all combination treatment arms in Part I and Part II.

Protocol/Amendment No.: 001-08

5.2.6 Trial Blinding

This is an open-label trial; therefore, the Sponsor, investigator and subject will know the treatment administered.

5.2.7 Replacement of Subjects During the DLT Evaluation Period

Subjects discontinuing within 21 days of the first dose due to reasons unrelated to study treatment will not be considered evaluable for DLTs and may be replaced. Subjects with a DLT within 21 days of the first dose should not be replaced. See Section 8.5.1 for description of safety analysis population.

5.3 Randomization or Treatment Allocation

Treatment allocation in the dose escalation and confirmation phase (Arms 1, 2, and 3) will be accomplished by nonrandom assignment. Enrollment into Arm 2 (MK-1454 with pembrolizumab combination therapy) will begin once:

- 1. At least 1 of the 3 triggering criteria are met in Arm 1 (MK-1454 monotherapy)
- 2. A dose escalation decision has been made
- 3. 2 dose levels within Arm 1 have been cleared by DLT evaluation

When Arm 1 and Arm 2 are open for enrollment, alternating subject assignment between Arm 1 and Arm 2, starting with Arm 1, will be via IWRS. For example, once the cohort of Arm 1 (MK-1454 monotherapy) and the dose cohort of Arm 2 (MK-1454 combination therapy with pembrolizumab) are open for enrollment, then the first subject will be allocated to Arm 1, the second subject will be allocated to Arm 2, the third subject will be allocated to Arm 1, etc. Subjects will be allocated to Arm 3 by nonrandom assignment via IWRS.

In the expansion phase, eligible subjects will be allocated to an appropriate open treatment arm by IWRS. For Cohorts A and B, 30 subjects will be allocated to each cohort. For Cohort C, 60 subjects will be allocated to treatment in total. There will be a cap at 15 subjects each for non MSI-H CRC and pancreatic cancer.

5.4 Stratification

No stratification based on age, sex, or other characteristics will be used in this trial.

5.5 Concomitant Medications/Vaccinations (Allowed and Prohibited)

Medications or vaccinations specifically prohibited in the exclusion criteria are not allowed during the ongoing trial. If there is a clinical indication for any medication or vaccination specifically prohibited during the trial, discontinuation from trial therapy or vaccination may be required. The investigator should discuss any questions regarding this with the Sponsor Clinical Director. The final decision on any supportive therapy or vaccination rests with the investigator and/or the subject's primary physician. However, the decision to continue the

Protocol/Amendment No.: 001-08

subject on trial therapy or vaccination schedule requires the mutual agreement of the investigator, the Sponsor and the subject.

All treatments that the investigator considers necessary for a subject's welfare may be administered at the discretion of the investigator and in keeping with the community standards of medical care. All concomitant medication will be recorded on the CRF including all prescription, OTC, herbal supplements, and IV medications and IV fluids. If changes occur during the trial period, then documentation of drug dosage, frequency, route, and date will also be included in the CRF.

All concomitant medications received within 30 days before the first dose of trial treatment through the 30-day Safety Follow-up Visit should be recorded. If subjects experience an SAE or ECI, all concomitant medications administered 30 days after the last dose of study intervention are to be recorded, as defined in Section 7.2.

Subjects are prohibited from receiving the following therapies during the Screening, and Treatment Phases of this trial:

- Immunotherapy not specified in this protocol.
- Antineoplastic systemic chemotherapy or biological therapy not specified in this protocol.
- Investigational agents not specified in this protocol.
- Radiation therapy; radiotherapy for symptom management is allowed beyond Cycle 2 upon approval by the Sponsor Medical Monitor or designee.
- Live vaccines within 30 days prior to the first dose of trial treatment and while participating in the trial. Examples of live vaccines include, but are not limited to, the following: measles, mumps, rubella, chickenpox, yellow fever, rabies, Bacillus Chalmette Guerin, and typhoid vaccine. Seasonal influenza vaccines for injection are generally killed virus vaccines and are allowed. However, intranasal influenza vaccines (eg, FluMist®) are live attenuated vaccines, and are not allowed.
- Systemic glucocorticoids for any purpose other than to modulate symptoms from an AE of suspected immunologic etiology. The use of physiologic doses of corticosteroids may be approved after consultation with the Sponsor.

Subjects who, in the assessment by the investigator, require the use of any of the aforementioned treatments for clinical management should be removed from the study. Subjects may receive other medications that the investigator deems to be medically necessary.

The Exclusion Criteria describe other medications which are prohibited in this trial.

There are no prohibited therapies during the Follow-up visits.

Protocol/Amendment No.: 001-08

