5.8.1 Discontinuation of Treatment

Discontinuation of treatment does not represent withdrawal from the trial.

As certain data on clinical events beyond treatment discontinuation may be important to the study, they must be collected through the subject's last scheduled follow-up, even if the subject has discontinued treatment. Therefore, all subjects who discontinue trial treatment prior to completion of the treatment will still continue to participate in the trial as specified in Section 6.0 - Schedule of Activities and Section 7.1.5.4 – Discontinued Subjects Continuing to be Monitored in the Trial.

Subjects may discontinue treatment at any time for any reason or be dropped from treatment at the discretion of the investigator should any untoward effect occur. In addition, a subject may be discontinued from treatment by the investigator or the Sponsor if treatment is inappropriate, the trial plan is violated, or for administrative and/or other safety reasons. Specific details regarding procedures to be performed at treatment discontinuation are provided in Section 7.1.4 – Other Procedures.

A subject must be discontinued from treatment but continue to be monitored in the trial for any of the following reasons:

- The subject or subject's legally acceptable representative requests to discontinue treatment.
- o Confirmed radiographic disease progression outlined in Section 7.1.2.7 (exception if the Sponsor approves treatment continuation).

27-Jul-2021 Confidential

087V73

Protocol/Amendment No.: 001-08

o The subject interrupts trial medication administration for more than 12 consecutive weeks.

- o Any progression or recurrence of any malignancy, or any occurrence of another malignancy that requires active treatment.
- o Intercurrent illness other than another malignancy as noted above that prevents further administration of treatment.
- o Recurrent Grade 2 pneumonitis.
- The subject is noncompliant with the protocol.
- The subject has a medical condition or personal circumstance which, in the opinion of the investigator and/or Sponsor, placed the subject at unnecessary risk from continued administration of study drug.
- The subject has a confirmed positive serum pregnancy test.
- O Side effects and/or concomitant medications required for treatment of HIV and/or its complications that are incompatible with continued study treatment (exceptions are permissible but should be discussed with the Sponsor).

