7.1.2.7.3 IWG Revised Response Criteria for Malignant Lymphomas

Response to treatment for lymphomas will continue to be assessed every 12 weeks that a subject remains in the trial.

Response to therapy will be assessed by CT or CT/PET, bone marrow biopsy, and clinical information including physical exam and symptoms, using the IWG Revised Response Criteria for Malignant Lymphomas [25]. Information collected includes:

1. At a minimum, thoracic, abdominal, and pelvic CT scans will be performed even if those areas were not initially involved because of the unpredictable pattern of recurrence in malignant lymphoma. Neck CT should be performed at Screening, and at follow-up visits if there is nodal involvement in the neck at screening. Fluorodeoxyglucose-PET scans may be obtained to supplement the anatomic

Protocol/Amendment No.: 001-08

imaging, and should always be collected at Screening, 12 weeks, 24 weeks, and when CR is suspected.

2. Unilateral bone marrow biopsy and aspirates will be performed at Screening, if not previously performed within 8 weeks prior to Screening with negative results. The bone marrow biopsy will be performed to confirm a CR if the subject was initially positive or if it is clinically indicated by new abnormalities in the peripheral blood counts or blood smear.

Response of lesions will be recorded on the eCRF based on the definitions in Table 16 as appropriate. Suspected relapse or disease progression must be confirmed by physical exam, laboratory assessments, repeat bone marrow biopsy [25], and CT scan. Subjects with suspected relapse or disease progression should continue to follow study procedures until they need another therapy. If a subject requires another therapy, date of treatment and type of treatment will be recorded, and they will then be removed from the trial.

Tumor progression is defined as $\geq 50\%$ increase from nadir in the sum of the products of diameters (SPD), of target lesions, or by growth of a single nodal target lesion, or by growth of nontarget lesions, or the appearance of new lesions, as defined in the IWG revised response criteria for malignancy lymphoma [25].

Table 16 Response Criteria for Malignant Lymphoma

Response	Physical			
Category	Examination	Nodal Masses	Spleen, Liver	Bone Marrow

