7.1.5.6 Survival Status Monitoring

All subjects, with the exception of those who withdraw consent or are lost to follow-up, will be followed up for survival and will be contacted approximately every 12 weeks (± 14 days) to monitor survival status. Subjects who experience confirmed disease progression or start a new anticancer therapy, will move into the Survival Follow-Up Phase and should be contacted by telephone every 12 weeks to assess for survival status until death, withdrawal of consent, or the end of the study, whichever occurs first.

To ensure current and complete survival data is available at the time of database locks, updated survival status may be requested during the course of the study by the Sponsor. For example, updated survival status may be requested prior to interim and/or final analysis. Upon Sponsor notification, all subjects who do not/will not have a scheduled study visit or study contact during the Sponsor-defined time period will be contacted for their survival

Protocol/Amendment No.: 001-08

status (excluding subjects who have withdrawn consent or have a previously recorded death event in the collection tool).

Every effort should be made to collect information regarding disease status until the start of new antineoplastic therapy, disease progression, death, or the end of the study.

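### Sections 5.5 and 7.1.2.7.3 take subjects who need a prohibited or further therapy out of the trial, while Sections 1.0, 5.8.1, 7.1.5.6 and 7.2.3.1 keep them in follow-up

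*Combined protocol and SAP*

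**What the plan says.** Two sentences remove subjects.

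- Section 5.5 lists therapies that are prohibited during screening and treatment: other immunotherapy, chemotherapy or biologics, other investigational agents, radiation, live vaccines and systemic glucocorticoids, with stated exceptions. It then says that subjects who "require the use of any of the aforementioned treatments for clinical management should be removed from the study".
- Section 7.1.2.7.3, on lymphoma response, says: "If a subject requires another therapy, date of treatment and type of treatment will be recorded, and they will then be removed from the trial". The sentence before it has subjects with suspected relapse or progression follow study procedures only up to that point.

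The follow-up rules point the other way.

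- Section 5.8.1: "Discontinuation of treatment does not represent withdrawal from the trial", and "all subjects who discontinue trial treatment prior to completion of the treatment will still continue to participate in the trial". Its list of reasons to stop treatment while staying monitored includes progression, or another malignancy, that needs active treatment.
- Sections 1.0 and 7.1.5.6 follow everyone for survival except those who withdraw consent or are lost. Section 7.1.5.6 adds that subjects who have confirmed progression or "start a new anticancer therapy, will move into the Survival Follow-Up Phase", with contact every 12 weeks.
- Section 7.2 collects AEs for 30 days after treatment. Section 7.2.3.1 collects SAEs and all deaths for 130 days, or 30 days if new anticancer therapy starts. Section 7.2.3.2 sets the same window for ECIs.
- Section 8.4.1 censors OS, for subjects not known to have died, at the last assessment or contact.

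**The concern.** For one and the same event, some sections end participation and others require follow-up to continue. A site that followed the removal sentences could not be cited for a deviation, yet it would omit data that other sections demand.

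Two things are at stake. AEs are part of the primary safety endpoint (Section 8.4.2), and their collection after treatment could be cut short. OS is exploratory (Section 3.3), but a subject removed alive is censored at that point. Where the trigger is a new anticancer therapy, the need for it commonly follows progression or toxicity, so the censoring would probably be related to prognosis. Section 7.1.4.1 itself warns that avoidable withdrawals can damage interpretability.

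**Working it through.** No figure in the plan depends on this point, so there is nothing to reproduce. The check sets the texts side by side.

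| Situation | Text that removes | Text that keeps | Can both be obeyed? |
|---|---|---|---|
| Part I lymphoma subject requires another therapy | 7.1.2.7.3 | 1.0, 5.8.1, 7.1.5.6, 7.2.3.1 | No. Study procedures end under one text, and survival contact begins under another |
| Subject on treatment requires chemotherapy or another prohibited anticancer therapy | 5.5 | 1.0, 5.8.1, 7.1.5.6, 7.2.3.1 | Not if 5.5 is read literally |
| Subject on treatment requires a prohibited therapy that is not anticancer, such as a live vaccine | 5.5 | 5.8.1 if treatment stops; the general rule in 7.1.5.6; 7.2.3.1 | Not if 5.5 is read literally |

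Section 5.5 also disagrees with itself. Its opening paragraph says only that "discontinuation from trial therapy or vaccination may be required". Its line on the follow-up period, "There are no prohibited therapies during the Follow-up visits", makes sense only if subjects who have stopped treatment are still being followed. The sentence between them speaks of the study, not of treatment. No precedence rule settles the matter.

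The exposure per subject, on the literal reading, can be bounded from the stated windows. Let t be the days from last dose to removal.

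- AE collection lost: max(0, 30 − t) days.
- SAE and ECI collection lost, new anticancer therapy started: max(0, 30 − t) days.
- SAE and ECI collection lost, no new anticancer therapy: max(0, 130 − t) days.
- Survival: every later 12-weekly contact.

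Two illustrative values of t, which are assumptions:

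| t | AE | SAE/ECI, new anticancer therapy | SAE/ECI, otherwise |
|---|---|---|---|
| 0 days | 30 | 30 | 130 |
| 21 days (one cycle) | 30 − 21 = 9 | 30 − 21 = 9 | 130 − 21 = 109 |

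These are upper bounds for one subject. A total would need the number of subjects who come to require such therapy, the number of lymphoma subjects, and how sites read the text. The documents give none of these.

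**The case against.** The best reply is that, in context, Section 5.5 means leaving trial therapy. Its opening paragraph says so, the prohibited list covers only screening and treatment, and follow-up visits are assumed to continue. The specific rules are also explicit: only two exemptions from survival follow-up exist, and the SAE windows run from the end of treatment. Section 7.1.4.1 has AEs present at withdrawal followed under Section 7.2. Section 7.2.3.1 keeps related SAEs reportable at any time. Section 7.1.5.6 lets the sponsor request survival status for anyone who has not died or withdrawn consent. A site that follows these rules loses nothing.

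Much of this stands, and it is why the point is a risk and not a finding of lost data. It does not rescue Section 7.1.2.7.3, where procedures run only until another therapy is needed and no treatment-only reading is offered.

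A reader might infer more than the documents support:

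- *Lymphoma and solid-tumor subjects are followed under different rules, which biases a pooled OS.* If Section 5.5 is read literally, it removes solid-tumor subjects too. No pooling of lymphoma with solid tumors for OS is described. The stated pooling adds Part I subjects who match a Part II tumor type.
- *Most progressing subjects are affected.* Confirmed progression has its own route in Sections 5.8.1 and 7.1.5.6, and Part I enrols subjects who have received, or could not tolerate, all treatment known to help.
- *Up to 130 days of SAE data are lost when next-line therapy starts.* In that case the window is 30 days.
- *Permitted radiotherapy or glucocorticoid use triggers removal.* The bullets in Section 5.5 carve those uses out.

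**Conclusion.** The contradiction is real and should be corrected. It is clearest in Section 7.1.2.7.3, which affects Part I lymphoma subjects only, and weaker in Section 5.5, where the surrounding text leans towards stopping trial therapy. The consequence is that AE and SAE collection and survival contact could end early, with probably informative censoring of exploratory OS. That rests on two assumptions: that some sites apply the wording literally, and that the therapy is needed because of progression or toxicity. The second does not hold for every item on the list, live vaccines for example, so it would go too far to say that the sickest subjects' events are lost. DLTs are counted in Cycle 1, so the dose-finding rules are largely untouched. The size of the effect cannot be computed from the documents.

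**What to change.** Amend one sentence in Section 5.5 and one in Section 7.1.2.7.3. In place of removal from the study or trial, state that the subject remains in the trial and is followed for AEs, SAEs, ECIs and survival under Sections 5.8.1, 7.1.5.4 to 7.1.5.6 and 7.2, with the existing windows unchanged. In Section 7.1.2.7.3, keep the recording of the date and type of the new therapy.

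Whether study treatment stops when such a therapy is needed is a separate matter. Sections 5.5, 5.2.3.4 and 5.8.1 must be reconciled on it by the sponsor. No clinical rule is proposed here.

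The cost is two sentences in an amendment and a note to sites. The end-of-treatment, 30-day and 12-weekly contacts are already in Sections 6.1.4 and 6.2.2, so there are no new visits and no change to sample size or analysis. If any subject has already left under this wording, the survival-status request in Section 7.1.5.6 can be used to update vital status, provided consent has not been withdrawn.
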